11.4 Causality

The investigator should have measures in place to promptly assess the relationship between adverse events and vaccination, in order to detect SAEs and group-related or trend-related adverse events associated with vaccination during the study. This allows for timely suspension or termination of the study to minimize harm to subjects.

General principles of relevance judgment:

Definitely Related: Evidence of vaccination with the study vaccine exists; the timing of the adverse event is reasonable relative to vaccination; the adverse event is more reasonably explained by the study vaccine than by other causes; active response upon re-vaccination; the adverse event is consistent with prior knowledge of this vaccine or similar vaccines.

Probably Related: Evidence of vaccination with the study vaccine exists; the timing

of the adverse event is reasonable relative to vaccination; the adverse event is more reasonably explained by the study vaccine than by other causes.

Possibly Related: Evidence of vaccination with the study vaccine exists; the timing of the adverse event is reasonable relative to vaccination; the adverse event cannot be ruled out as being caused by the study vaccine, although other causes are also possible.

Unlikely Related: Evidence of vaccination with the study vaccine exists; the adverse event is more likely to be caused by other factors; negative or uncertain response upon re-vaccination.

Definitely Unrelated: The subject did not receive the study vaccine; or the timing of the adverse event is inconsistent with vaccination; or there is another significant cause that can explain the adverse event.

For statistical analysis, "Definitely Related," "Probably Related," and "Possibly Related" are considered adverse events "related" to the study vaccine, while "Unlikely Related" and "Definitely Unrelated" are considered adverse events "unrelated" to the study vaccine.

As the investigator's understanding of AE/SAE is a progressive process, the initial report may contain uncertain causality information. As information accumulates or updates in subsequent visits, the investigator may revise the initial causality assessment. In such cases, AE/SAE follow-up is required, especially for SAEs, to ensure that relevant information is updated.

12. Appendix: Definitions and Supportive Operational Details

12.1 Contraception and Pregnancy Testing

12.1.1 Definitions Related to Fertility

Women of Childbearing Potential: Women from menarche until menopause are considered capable of childbearing unless it has been confirmed that they have undergone a hysterectomy, bilateral salpingectomy, and bilateral oophorectomy.

Postmenopausal Women: Women who have ceased normal menstruation for 12 consecutive months with no other medical cause.

12.1.2 Contraception

Female subjects must not be pregnant or breastfeeding. Women of childbearing potential (WOCBP) must use reliable contraceptive methods and should not have plans for pregnancy or childbirth within 8 months. Pregnancy is an exclusion criterion for each vaccine dose, and WOCBP are required to use effective contraception for 3 months following the first vaccine dose.

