Age	Aged 50 and older				
Sex	Male and female (relatively balanced)				
Inclusion criteria	
 1. Age 50 years or older on the day of enrollment, regardless of gender, and able to provide legal identification. 2. Able to understand the trial procedures, voluntarily agree to participate in the study, and sign the "Informed Consent Form." 3. Female subjects are not pregnant or lactating. Female subjects with childbearing potential should take reliable contraceptive measures, and have no pregnancy and fertility plan within 8 months; 4. Axillary temperature \leq 37.0°C/99.0°F on the day of enrollment. 5. Able to attend all scheduled follow-up visits and able to comply with protocol requirements. 				

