4.3 Inclusion criteria

- 1) Age 50 years or older on the day of enrollment, regardless of gender, and able to provide legal identification.
- 2) Able to understand the trial procedures, voluntarily agree to participate in the study, and sign the "Informed Consent Form."
- 3) Female subjects are not pregnant or lactating. Female subjects with childbearing potential should take reliable contraceptive measures, and have no pregnancy and fertility plan within 8 months;
- 4) Axillary temperature $\leq 37.0^{\circ}\text{C}/99.0^{\circ}\text{F}$ on the day of enrollment.
- 5) Able to attend all scheduled follow-up visits and able to comply with protocol requirements.

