7.5 Pregnancy and Postpartum Information

7.5.1 Subjects Who Become Pregnant During the Study

Pregnancy is an exclusion criterion for each vaccine dose, and women of childbearing potential are required to use effective contraception for eight months following the first vaccine dose. However, accidental pregnancies may still occur during participation. Any pregnancy occurring from the time of vaccination through six months after full immunization must be reported, and the investigator is required to complete a "Pregnancy Event Report Form."

Researchers will closely follow pregnant subjects to obtain pregnancy outcome information (e.g., details of delivery and newborn status, or termination of pregnancy) and update the "Pregnancy Event Report Form."

Pregnancy itself is not considered an AE, but any complications during pregnancy are considered AEs and, in certain cases, may be classified as SAEs, such as spontaneous

abortion, stillbirth, or congenital anomalies in the infant. Elective abortions due to personal choice, where no fetal abnormalities are present, are not considered adverse events.

Handling Pregnancy Events During Vaccination:

If pregnancy occurs after the first dose but before the completion of the full vaccination course, the subject should not receive the second dose until the pregnancy ends (whether full-term, miscarriage, or abortion). The investigator will maintain regular contact with the subject for pregnancy assessments.

If pregnancy is discovered after the subject has completed the full vaccination course, the subject may complete study visits per the protocol and investigator discretion.

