11.1 Further Details and Explanations on the Definition of AE

Adverse Event (AE): Any unfavorable medical occurrence in a subject after receiving the study product, which may present as symptoms, signs, diseases, or laboratory abnormalities. These events do not necessarily have a causal relationship with the study product.

Pregnancy-related events are not reported as AEs.

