12.1.3 Pregnancy Testing

WOCBP (all women from menarche until menopause) must undergo a urine pregnancy test prior to each vaccination. The urine pregnancy test must be performed on the day of vaccination and before vaccination takes place. No sample storage is required after testing.

Pregnancy is an exclusion criterion for each vaccine dose, and WOCBP are required to use effective contraception for 8 months after the first vaccine dose. However, it is still possible for participants to become unintentionally pregnant during the study. Any pregnancy occurring after vaccination and throughout the study period should be reported, and the investigator must complete a "Pregnancy Event Report Form."

Researchers must closely follow up with pregnant subjects to obtain information on pregnancy outcomes (e.g., details of childbirth and neonatal status or pregnancy termination) and update the "Pregnancy Event Report Form."

Pregnancy itself is not considered a serious adverse event; however, any complications during pregnancy will be regarded as adverse events and may be considered serious adverse events in certain cases, such as spontaneous abortion, stillbirth, fetal death, and congenital abnormalities in the infant. Elective termination of pregnancy due to maternal choice, in the absence of fetal abnormalities, is not considered an adverse event.

Management of Pregnancy Events During Vaccination:

- If pregnancy occurs after the first dose but before the vaccination schedule is complete, the subject must not receive the second dose until the pregnancy has concluded (e.g., full-term birth, miscarriage, or abortion). The investigator will maintain regular contact with the subject to conduct pregnancy assessments.
- If pregnancy is discovered after the subject has completed the full vaccination schedule, the subject may complete study visits according to the trial protocol and at the discretion of the investigator.

13. Disclosure and Publication of Data

Upon completion of this study, if the results are to be disclosed and/or published, both active and negative results will be disclosed and/or published. Subject confidentiality will be maintained in accordance with privacy protections.

14. Reference

1. WHO. Recommendations to assure the quality, safety and efficacy of recombinant human papillomavirus virus-like particle vaccines[J].2006.

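### Section 12.1.2 sets 3 months of contraception after the first dose where 7.5.1 and 12.1.3 set 8, and the pregnancy line in 11.1 needs rewording to agree with the AE rules elsewhere

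*Protocol*

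**What the plan says.** **Contraception.** Three sections of the protocol give a duration for women of childbearing potential:

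- Section 12.1.2: "WOCBP are required to use effective contraception for 3 months following the first vaccine dose".
- Section 12.1.3: "WOCBP are required to use effective contraception for 8 months after the first vaccine dose".
- Section 7.5.1: "women of childbearing potential are required to use effective contraception for eight months following the first vaccine dose".

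An 8-month figure also appears for pregnancy plans. Inclusion criterion 3 (section 4.3, repeated in the synopsis) reads "Female subjects with childbearing potential should take reliable contraceptive measures, and have no pregnancy and fertility plan within 8 months". In section 12.1.2, the sentence before the 3-month rule says that these women "should not have plans for pregnancy or childbirth within 8 months".

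**AE status of pregnancy events.** Section 11.1 ends its definition of an AE with the line "Pregnancy-related events are not reported as AEs". Section 7.5.1 says that "any complications during pregnancy are considered AEs and, in certain cases, may be classified as SAEs" and gives spontaneous abortion, stillbirth and congenital anomaly as examples. Section 12.1.3 says the same in substance. Section 7.4.1 makes congenital anomaly or birth defect an SAE criterion and sends the reader to Appendices 11.1 and 11.2 for detail. Section 7.4.8 excludes only pregnancy itself from AEs.

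**The concern.** These are working instructions to sites, not background. The three contraception sentences cover the same women, start from the same dose and are equally mandatory, so they are one rule stated with two numbers. A site that takes its duration from 12.1.2 and a site that takes it from 7.5.1 or 12.1.3 would apply different requirements.

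The line in 11.1 raises a second question. SAE incidence from the first dose to 6 months after full immunization is a named safety endpoint (section 2.2.2), and section 7.4.4 requires SAEs to be reported within 24 hours. A site that took 11.1 at its broadest could leave a pregnancy complication out of AE and SAE reporting when 7.5.1 and 12.1.3 would include it. The cross-reference from 7.4.1 to 11.1 makes that reading easier to reach.

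**Working it through.** No sample size, power or error rate enters here. The check compares texts and adds some calendar arithmetic.

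**Inputs**

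- Month = 30 days (Definitions of Terms).
- Second dose at D30 (experimental) or D60 (control), window -2/+7 days (section 5.1.7 and Schedule of Activities).
- Pregnancies collected from the first dose to 6 months after full immunization (sections 3.1.3.2, 5.1.9.2 and 7.5.1).

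**End of each contraception period, counted from the first dose at D0**

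- Section 12.1.2: 3 × 30 = D90.
- Sections 7.5.1 and 12.1.3: 8 × 30 = D240.
- Difference: 240 − 90 = 150 days.

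**Nominal end of pregnancy collection**

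- Experimental: 30 + 6 × 30 = D210.
- Control: 60 + 6 × 30 = D240.

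**Distance from the end of each contraception period to the end of collection**

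| Period | Ends | Experimental (D210) | Control (D240) |
|---|---|---|---|
| 3 months | D90 | 210 − 90 = 120 days before | 240 − 90 = 150 days before |
| 8 months | D240 | 240 − 210 = 30 days after | same day |

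In the control arm, D90 is 90 − 60 = 30 days after the nominal second dose, or 90 − 67 = 23 days after a dose given at the end of its window. These figures measure the discrepancy; they do not show which period was intended.

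**Which sections give 8 months for contraception.** Two do: 7.5.1 and 12.1.3. Inclusion criterion 3 and the earlier sentence of 12.1.2 require reliable contraception but attach the 8 months to pregnancy plans. They fit an 8-month period without stating one for contraception.

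**AE status, side by side**

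| Section | Pregnancy itself | Complications |
|---|---|---|
| 7.4.1 | not addressed | congenital anomaly is an SAE criterion |
| 7.4.8 | not an AE | not addressed |
| 7.5.1 | not an AE | AE, possibly SAE |
| 12.1.3 | not an SAE | AE, possibly SAE |
| 11.1 | not reported as an AE | not reported as AEs, if read literally |
| 11.2 | not addressed | not among the listed exclusions from SAE |

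Only the last column of the 11.1 row is out of line, and only if its wording is taken to cover complications.

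**The case against.** On contraception, the best reply is that the 3 in 12.1.2 is an isolated figure. The sentence before it already speaks of 8 months, so a reader of that section alone still meets the longer horizon. This makes a slip plausible, but it does not remove the conflict: the sentence that sets the duration still says 3 months.

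On AE reporting, the reply is stronger. Sections 3.1.3.2 and 5.1.9.1 name pregnancy-related events beside SAEs as a separate stream of data. Section 5.1.9.2 sends the reader to section 7.5 for how they are reported and assessed. In that usage, 11.1 may mean only that a pregnancy goes on its own report form and is not logged as an AE, which agrees with 7.4.8. This stands as a reasonable reading. What remains is that 11.1 carries no such limit, whereas 7.4.8 and 7.5.1 confine their exclusion to pregnancy itself.

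The effect is also small. All participants are 50 or older, pregnancies are collected for the same period whichever contraception text is followed, and SAE incidence is tabulated without a hypothesis test (section 8.4.4). All of this stands.

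**Conclusion.** The contraception conflict is established: 12.1.2 says 3 months and 7.5.1 and 12.1.3 say 8, which is D90 against D240. It concerns an instruction that bears on participant safety and should be corrected. The 11.1 point is a request for clearer wording, because the conflict depends on a literal reading of one line.

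A reader might infer more than the documents support:

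- *That a third section sets 8 months of contraception.* Inclusion criterion 3 attaches the 8 months to pregnancy plans.
- *That the protocol firmly makes pregnancy complications both reportable and not reportable.* The narrower reading of 11.1 is open, and 7.4.1, 7.5.1 and 12.1.3 all keep complications or their outcomes in.
- *That participants are told conflicting things.* The consent form was not available, so this cannot be judged.
- *That pregnancy data would be lost under the shorter period.* The collection window does not depend on the contraception period.

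The calendar figures assume nominal visit days. The protocol gives no number of participants of childbearing potential; that it will be small is inferred from the age criterion. The primary analysis, sample size and power are unaffected.

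**What to change.** Reconcile 12.1.2 with 7.5.1 and 12.1.3 so that one contraception period, with one starting point, appears throughout, and check it against the pregnancy-plan wording in inclusion criterion 3 and in 12.1.2.

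Reword the pregnancy line in 11.1 so that it agrees with 7.4.1, 7.4.8, 7.5.1 and 12.1.3, and so that a site following the cross-reference from 7.4.1 finds the same rule for pregnancy itself and for its complications.

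Which period and which reporting rule apply is for the sponsor to settle. The cost is a wording amendment; no visit, sample or analysis changes.

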12.1.3 Pregnancy Testing

WOCBP (all women from menarche until menopause) must undergo a urine pregnancy test prior to each vaccination. The urine pregnancy test must be performed on the day of vaccination and before vaccination takes place. No sample storage is required after testing.

Pregnancy is an exclusion criterion for each vaccine dose, and WOCBP are required to use effective contraception for 8 months after the first vaccine dose. However, it is still possible for participants to become unintentionally pregnant during the study. Any pregnancy occurring after vaccination and throughout the study period should be reported, and the investigator must complete a "Pregnancy Event Report Form."

Researchers must closely follow up with pregnant subjects to obtain information on pregnancy outcomes (e.g., details of childbirth and neonatal status or pregnancy termination) and update the "Pregnancy Event Report Form."

Pregnancy itself is not considered a serious adverse event; however, any complications during pregnancy will be regarded as adverse events and may be considered serious adverse events in certain cases, such as spontaneous abortion, stillbirth, fetal death, and congenital abnormalities in the infant. Elective termination of pregnancy due to maternal choice, in the absence of fetal abnormalities, is not considered an adverse event.

Management of Pregnancy Events During Vaccination:

- If pregnancy occurs after the first dose but before the vaccination schedule is complete, the subject must not receive the second dose until the pregnancy has concluded (e.g., full-term birth, miscarriage, or abortion). The investigator will maintain regular contact with the subject to conduct pregnancy assessments.
- If pregnancy is discovered after the subject has completed the full vaccination schedule, the subject may complete study visits according to the trial protocol and at the discretion of the investigator.

13. Disclosure and Publication of Data

Upon completion of this study, if the results are to be disclosed and/or published, both active and negative results will be disclosed and/or published. Subject confidentiality will be maintained in accordance with privacy protections.

14. Reference

1. WHO. Recommendations to assure the quality, safety and efficacy of recombinant human papillomavirus virus-like particle vaccines[J].2006.
